4.0 TREATMENT PLAN

4.1 Overview

Patients will be treated with B 45 mg two times daily and HCQ 400 mg twice daily beginning on day 1. The dose of HCQ is based on an ongoing Phase 1 trial, and may be modified in a future amendment prior to the first patient enrolled. Efforts will be made to ensure dose homogeneity throughout the trial. Treatment will be administered on an outpatient basis on a 28 day cycle. Reported adverse events and potential risks for HCQ and B are described in Section 6. Appropriate dose modifications for HCQ and B are described in Sections 5 and 6. No investigational or commercial agents or therapies other than those described below may be administered with the intent to treat the patient's malignancy.

4.2 Hydroxychloroquine administration

Hydroxychloroquine is an oral medication, requiring the patients on study to keep a study diary. Diary must be submitted at each clinic visit.

Hydroxychloroquine should be obtained commercially. The starting dose for HCQ will be 400. Tablets of HCQ are available in 200 mg strength. HCQ will be administered in divided doses (every 12 hours) with or without food. To enhance compliance and assist in pharmacokinetic analysis, the two daily doses of HCQ should be taken 12 hours apart, for example, 9 AM and 9 PM, and documented clearly on the patient calendar. Modification of the schedule in case of GI symptoms is allowed. Missed doses do not need to be replaced. On days of clinic visits, patients will be asked the date / time / dose of last HCQ taken. This information will be documented on the CRF. Patients will be asked to take HCQ continuously, as prescribed.

4.3 Binimetinib administration

The starting dose for B is 45 mg BID. B will be administered in divided dose (every 12 hours) on either an empty or full stomach. The two daily doses of B should be taken 12 hours apart, for example, 9 AM and 9 PM.

4.4 Concomitant Medication and Procedures

Because HCQ has known effects on P450 enzymes, patients requiring anti-convulsants may be treated with any of the non-enzyme inducing anti-convulsants which include: felbamate, valproic acid, gabapentin, lamotrigine, tiagibine, topiramate, or levetiracetam. Zonisamide is not recommended as this drug accumulates in red blood cells where HCQ also accumulates. For nausea aprepitant should be avoided. Radiation therapy to the surgical bed with gamma knife radiotherapy while on treatment is allowed for surgically resected brain metastases. Gamma knife for new CNS lesions may be performed while on study, but further of treatment of these patients will be considered treatment beyond progression (see Section 4.5). Binimetinib does not need to be taken fasting. All other concomitant medications are permitted, but P-gp and BCRP inhibitors are to be administered with caution.

4.5 Duration of Protocol Treatment and Follow-up

Treatment will continue until disease progression and may continue at the discretion of the treating physician in consultation with the Principal Investigator, if there is an isolated progression. Treatment may also be discontinued for adverse events that delay treatment greater than 28 days and as outlined in Toxicities and Dose Modifications. Please refer to Off Treatment/Off Study for additional reasons for study withdrawal. Subjects will be evaluated for at least 6 months after discontinuation of study treatment and will be followed for a minimum of one year from the start of treatment, unless disease progression is reported prior to one year. One year survival information will be extracted from the medical record or by phone call for subjects who have discontinued protocol treatment and completed the 6 month follow-up evaluations prior to one year from the start of treatment.

5.0 TOXICITY CRITERIA, MONITORING, DOSE DELAYS AND MODIFICATIONS

5.1 Toxicity Criteria

This study will utilize the CTCAE version 5 for toxicity and Adverse Event Reporting. A copy of the CTCAE version 5.0 can be downloaded from the CTEP home page (http://ctep.cancer.gov). All appropriate treatment areas should have access to a copy of the CTCAE version 5.0.

5.2 Dose Delays

Major Events are grade 3 and 4 hematologic and non-hematologic toxicities that are not treatment -related. Treatment should be delayed for major events if it may further complicate the

non-treatment related event. If a major event requires a delay of treatment, treatment must be delayed until toxicity is resolved (\leq Grade 2 or \leq Baseline). For treatment-related toxicities and major events, if toxicity is not resolved in \leq 28 days, patient will be taken off treatment, unless there is an exception granted by the medical monitor.

5.3 Toxicities and Dose Modifications

Guidelines for specific toxicities are outlined below, but general guidelines for toxicities not listed are provided in Table 5. Of note, if a toxicity is attributable only to one of the investigational drugs, the other investigational agent can be continued if tolerated.

General Dose modification guidelines for binimetinib for toxicities attributable to only binimetinib. These are general guidelines but for specific toxicities dose modification instructions may be different Doses of binimetinib should be adjusted for AEs throughout the study (see Table 1 Recommended Dose Levels). In general, doses should not be reduced or interrupted for Grade 1 AEs unless the AE is a specific ocular AE referred to in the Recommended Dose Modifications Table (see Table 2) but treatment to control symptoms should be provided as appropriate, if applicable.

An individual patient may have their dose of binimetinib reduced to the dose levels in Table 1 below:

Table 1 Recommended Dose Levels

	Binimetinib (mg BID)
Starting Dose	45
Dose Level -1	30
Dose Level -2	15

The lowest recommended dose level of binimetinib is 15 mg BID. When the AE that resulted in a dose reduction improves to and remains stable at the patient's baseline level for a minimum of 14 days, the dose can be re-escalated to the next dose level at the discretion of the Investigator, provided there are no other concomitant toxicities that would prevent drug re-escalation. There is no limit to the number of times the patient can have their dose reduced or re-escalated, however:

- No dose re-escalation of binimetinib is allowed after a dose reduction due to LVEF dysfunction
- No dose re-escalation of binimetinib is allowed after a dose reduction due to retinal toxicity ≥ Grade 2.

Please refer to Dose Modification Table for recommended dose modifications for binimetinib, if applicable, based on the occurrence of treatment-related AEs.

Table 2 Recommended Dose Modifications

In all cases except retina disorders, HCQ may be continued at the discretion of the treating physician

Severity of Adverse Event	Dose Modifications		
Cardiomvopathv			
Asymptomatic, absolute decrease in LVEF of > 10% from baseline that is also	Withhold binimetinib for up to 4 weeks, evaluate LVEF every 2 weeks.		
below the LLN	Resume binimetinib at a reduced dose if the following are present:		
	 LVEF is at or above the LLN and Absolute decrease from baseline is 10% or less and 		
	Patient is asymptomatic.		
	If LVEF does not recover within 4 weeks permanently discontinue binimetinib.		
Grade 3-4 (Symptomatic congestive heart failure or absolute decrease in LVEF of > 20% from baseline that is also below LLN)	Permanently discontinue binimetinib. Closely monitor LVEF until resolution or up to 16 weeks.		
Venous Thromboembolism			
Uncomplicated DVT or PE	Withhold binimetinib.		
	 If improves to Grade 0-1, resume at a reduced dose. 		
	 If no improvement, permanently discontinue binimetinib. 		
Life threatening PE	Permanently discontinue binimetinib.		
Serous Retinopathy			
Symptomatic serous retinopathy/ Retinal pigment epithelial detachments	 Withhold binimetinib for up to 10 days. If improves and becomes asymptomatic, resume at the same dose. If not improved, resume at a lower dose level or permanently discontinue binimetinib. 		
Retinal Vein Occlusion (RVO) Any Grade	Permanently discontinue binimetinib.		
Uveitis			
Grade 1-3	If Grade 1 or 2 does not respond to specific ocular therapy, or for Grade 3 uveitis, withhold binimetinib for up to 6 weeks.		
	 If improved, resume at same or reduced dose. If not improved, permanently discontinue binimetinib. 		
Grade 4	Permanently discontinue.		

Severity of Adverse Event	Dose Modifications			
Other Eye Disorders (i.e., Non-retinal Eve	ents, non-Uveitis Events			
Grade 1-2	Maintain dose level of binimetinib and increase			
	frequency of ophthalmic monitoring to at least			
	every 14 days until stabilization or resolution.			
Grade 3	Interrupt dosing of binimetinib and refer patient to			
	ophthalmologist within 7 days.			
	• If resolved to Grade ≤ 1 in ≤ 21 days, resume			
	treatment at 1 reduced dose level of			
	binimetinib.			
	 If not resolved to Grade ≤ 1 in ≤ 21 days, 			
	permanently discontinue binimetinib and close			
	follow-up with ophthalmic monitoring until			
	stabilization or resolution.			
Grade 4	Permanently discontinue binimetinib and			
	immediate follow-up with ophthalmic monitoring			
	until stabilization or resolution.			
Interstitial Lung Disease				
Grade 2	Withhold binimetinib for up to 4 weeks.			
	• If improved to Grade 0-1, resume at a reduced			
	dose.			
	• If not resolved within 4 weeks, permanently			
Orada 2 an Orada 4	discontinue.			
Grade 3 of Grade 4	Permanentiy discontinue.			
Hepatotoxicity				
Grade 2 AST or ALT increased	Maintain binimetinib dose.			
	If no improvement within 2 weeks, withhold			
	binimetinib until improved to Grade 0-1 or to			
	pretreatment/baseline levels and then resume at			
	the same dose.			
Grade 3 or 4 AST or ALT increased	See Other Adverse Reactions			
Rhabdomyolysis or Creatine Phosphokina	ase (CPK) elevations			
Grade 4 asymptomatic CPK elevation or	Withhold binimetinib dose for up to 4 weeks.			
Any Grade CPK elevation with	If improved to Grade 0-1 resume at a reduced			
symptoms or with renal impairment	dose.			
	If not resolved within 4 weeks, permanently			
	discontinue binimetinib.			
Dermatologic				
Grade 2	It no improvement within 2 weeks, withhold until			
	Grade 0-1. Resume at same dose if first			
	occurrence or reduce dose if recurrent.			
Grade 3	Withhold until Grade 0-1. Resume at same dose i			
	TIRST OCCURRENCE OF REDUCE dose if recurrent. If			
	recurrent and already on dose level -2, resume at			
Crada 4	Inal dose.			
Graue 4	Permanentiy discontinue			
Grade 1.2	Maintain doca loval of hinimatinih Dramativ			
Glaue 1-2	institute antiemetic massure			

Severity of Adverse Event Grade 3	Dose Modifications Interrupt dosing of binimetinib until resolved to Grade ≤ 1. Then resume treatment at 1 reduced dose level of binimetinib. Resume treatment with binimetinib at the current dose if, in the judgment of the Investigator, the toxicity is considered to be unrelated to binimetinib, or at 1 reduced dose level.		
	Note: Interrupt dosing of binimetinib for \geq Grade 3 vomiting or Grade 3 nausea only if the vomiting or nausea cannot be controlled with optimal antiemetics (as per local practice).		
Grade 4	Permanently discontinue binimetinib.		
Other Adverse Reactions (including haemorrhage)			
Recurrent Grade 2 or	Withhold for up to 4 weeks.		
First occurrence of any Grade 3	 If improves to Grade 0-1 or to pretreatment/baseline levels, resume at reduced dose. If no improvement, permanently discontinue. 		
First occurrence of any Grade 4	 Permanently discontinue or withhold for up to 4 weeks. If improves to Grade 0-1 or to pretreatment/baseline levels, then resume at a reduced dose. If no improvement, permanently discontinue. 		
Recurrent Grade 3	Consider permanently discontinuing.		
Recurrent Grade 4	Permanently discontinue.		

Investigators should always err on the side of caution in these settings if treatment-related toxicity is a possibility.

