-Slit-lamp biomicroscopic examination of the anterior segment structures: eyelid margins, conjunctiva, sclera, cornea, anterior chamber, iris, lens, and anterior vitreous

-Intraocular pressure (IOP) measurement

-Following dilation of the pupil, continued slit-lamp biomicroscopic examination of anterior segment structures with clinical grading of lens opacity

-Fundus slit-lamp biomicroscopic examination, including use of accessory diagnostic lenses, to view the vitreous, retina, macula, vasculature, and optic nerve

4-if changes on exam or ancillary testing are noted, fundus photography and autofluorescence should be utilized if clinically indicated.

Footnotes (a-e)

- **a-** Within 56 days of starting therapy
- **b-** +/- 1 week to allow for scheduling difficulties
- c- +/- 2 weeks to allow for scheduling difficulties
- d- After 2 years patients will continue to be followed every six cycles (months). At the half-year follow-ups (e.g. 2.5 y, 3.5 y, etc), exams will comprise the same components as the 1.5 y exam. At the annual follow-ups (e.g. 3y, 4y, etc), the exam will comprise the same components as the 2 year exam.
- e- If end of study occurs within 3 cycles (months) of the most recent scheduled exam, no additional testing is required unless ophthalmic concerns played a role in discontinuation in which case a full end of study exam is conducted. If end of study falls outside of this timeframe, the end of study eye exam should be captured when feasible.

CTCAE Grade ^a	Adverse Event Management	Action and Dose Modification
Grade 1 ^b	 Consult ophthalmologist within 7 days of onset 	 If dilated fundus examination cannot be performed within 7 days of onset, interrupt binimetinib and hydroxychloroquine until RVO, and visual field deficit can be excluded by retina specialist/ophthalmologist.
		 If and RVO excluded, continue (or restart) binimetinib and HCQ at same dose level
		If RVO diagnosed: Permanently discontinue binimetinib and report as SAE.
Grade 2 and Grade 3	 Consult ophthalmologist immediately Interrupt binimetinib and HCQ. 	 If RVO excluded, restart binimetinib and HCQ at same dose level.
		If RVO diagnosed: Permanently discontinue binimetinib and report as SAE
Grade 4	Consult ophthalmologist immediatelyInterrupt binimetinib and HCQ.	• If visual field deficit and RVO excluded, may consider restarting binimetinib at same or reduced dose after discussion with study medical monitor

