		 If RVO or visual field deficit diagnosed, permanently discontinue binimetinib and report as SAE.

Table 4 Management and Dose Modification Guidelines for Visual Changes and/or Ophthalmic Examination Findings

Abbreviations: RPED = retinal pigment epithelial detachment; CTCAE = Common Terminology Criteria for Adverse Events; RVO= retinal vein occlusion; SAE = serious adverse event

- a. Refers to CTCAE Version 5.0 'Eye disorders Other, specify'
- b. If visual changes are clearly unrelated to study treatment (e.g., allergic conjunctivitis), monitor closely but ophthalmic examination is not required.

Table 5 Recommended dose modifications for binimetinib for retinal pigment epithelial detachments (RPED)

CTCAE Grade	A	ction and Dose Modification
Grade 1 RPED (Asymptomatic; clinical or diagnostic observations only)	•	Continue treatment with retinal evaluation each cycle (monthly) until resolution. If RPED worsens follow instructions below
Grade 2-3 RPED (Symptomatic with	•	Interrupt binimetinib and hydroxychloroquine
mild to moderate	•	Retinal evaluation each cycle (monthly)
decrease in visual acuity; limiting instrumental ADL)	•	If improved to ≤ Grade 1, restart binimetinib at lower dose or discontinue in patients taking lowest dose

Table 6 Management of Ocular Toxicities

Ocular Toxicity	Uveitis, conjunctivitis	Retinal Vein occlusion, retinal pigment epithelial detachment (RPED), papilledema.	Visual field deficits
Action	Continue all therapies as long as effective local therapies can control inflammation	See table 3, 4, 5	Discontinue HCQ

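### Tables 2 and 5 give different binimetinib restart doses after symptomatic retinal pigment epithelial detachment, and no reduced hydroxychloroquine dose is defined

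*Combined protocol and SAP*

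**What the plan says.** **Binimetinib after RPED**

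- Section 5.3, Table 2, has a row for serous retinopathy that names symptomatic RPED. Binimetinib is withheld for up to 10 days. On recovery: "If improves and becomes asymptomatic, resume at the same dose". Otherwise: "If not improved, resume at a lower dose level or permanently discontinue binimetinib".
- Section 5.3.1, Table 5, is the RPED table. Grade 1 is asymptomatic, and treatment continues with monthly retinal evaluation. For grade 2-3 (symptomatic, with reduced acuity) it says: "Interrupt binimetinib and hydroxychloroquine". Then: "If improved to ≤ Grade 1, restart binimetinib at lower dose or discontinue in patients taking lowest dose". It has no grade 4 row.
- Table 6 sends RPED to Tables 3, 4 and 5. The grade 2-3 row of Table 4 says: "If RVO excluded, restart binimetinib and HCQ at same dose level". Its grade 4 row allows restart to be considered only once retinal vein occlusion (RVO) and visual field deficit are excluded, after discussion with the medical monitor.
- Section 5.3 introduces its general binimetinib rules as being for toxicities due to binimetinib alone, and adds: "These are general guidelines but for specific toxicities dose modification instructions may be different". On re-escalation: "No dose re-escalation of binimetinib is allowed after a dose reduction due to retinal toxicity ≥ Grade 2".

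**HCQ reductions**

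- Section 5.3.2 permits up to two reductions and twice names Table 5 as the source of the reduced dose. It also says that signs of retinal toxicity should lead to drug discontinuation and an eye evaluation.
- Section 4.1 sets the start at 400 mg twice daily and says that HCQ modifications are in Sections 5 and 6. Section 4.2 gives the tablet strength as 200 mg.

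**The concern.** A dose-modification table should give one answer for one patient. Here an investigator whose patient has recovered from symptomatic RPED finds a same-dose instruction in one table and a lower-dose instruction in another. The choice lasts, because a reduction made for this reason cannot later be undone.

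An investigator told to reduce HCQ finds no dose to reduce to and has to improvise one.

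What is at stake is the safety of individual patients and the consistency of dosing. Section 4.1 asks for homogeneous dosing across the trial, safety and tolerability is a primary objective, and Section 5.3.1 treats the eye findings as an important product of the study. Section 10.4 lists dosing errors among the deviations to be submitted, so a patient dosed correctly under one table may look misdosed under the other.

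**Working it through.** The plan states no figure for this point, so the check is a comparison of rules followed by simple arithmetic.

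**1. Do Tables 2 and 5 describe the same situation?** Table 2's trigger is symptomatic RPED. Table 5's grade 2-3 row is also symptomatic, with the added detail of mild to moderate loss of acuity and limits on instrumental daily activities. Table 2 is the wider of the two, and Table 5 grade 2-3 falls within it. For recovery, Table 2 requires the patient to be asymptomatic. Table 5 requires grade 1 or less, and it defines grade 1 as asymptomatic. For a grade 2-3 event that becomes asymptomatic, both rules apply and they differ.

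**2. Size of the difference.** Inputs are the Table 1 levels: 45, 30 and 15 mg BID. Daily dose = 2 × BID dose. Reduction = 1 − (lower ÷ current).

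| Dose at onset | Table 2 on recovery | Table 5 on recovery | Daily dose | Reduction |
|---|---|---|---|---|
| 45 mg BID | 45 mg BID | 30 mg BID | 90 vs 60 mg | 1 − 30/45 = 33% |
| 30 mg BID | 30 mg BID | 15 mg BID | 60 vs 30 mg | 1 − 15/30 = 50% |
| 15 mg BID | 15 mg BID | discontinue | 30 vs 0 mg | 100% |

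**3. If RPED does not improve.** Table 2 holds for up to 10 days, then allows a lower dose or permanent discontinuation. Table 5 allows restart only on improvement and sets no end to the hold. The general limit of 28 days in Sections 5.2 and 9.4.7 then applies.

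**4. Does Table 4 add a conflict?** Table 6 routes RPED to it, and its grade 2-3 row restarts both drugs at the same dose. But that row is triggered by exclusion of RVO, not by recovery, and a footnote ties its grading to the residual CTCAE term for other eye disorders. It is a secondary inconsistency. Its grade 1 row has words missing in the text available and is not relied on.

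**5. HCQ after RPED.** Three instructions are not reconciled. Table 5 interrupts HCQ and gives no restart rule. Table 4 restarts it at the same dose. Section 5.3.2 says that retinal toxicity should prompt discontinuation. The heading of Table 2 also excludes retinal disorders from the physician's discretion to continue HCQ.

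**6. HCQ dose levels.** Table 5 concerns binimetinib for RPED, Table 1 lists binimetinib only, and Section 6 has no HCQ reductions. Tables 1 to 8 are all present in the text and none gives a reduced HCQ dose. Section 5.3 also cites Table 5 as the general guideline for unlisted toxicities, which it is not.

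As an illustration, the start is 2 × 400 = 800 mg/day. Assuming whole 200 mg tablets with at least one every 12 hours, the reduced options are:

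- 400 + 200 = 600 mg/day, which is 1 − 600/800 = 25% below the start
- 200 + 200 = 400 mg/day, which is 1 − 400/800 = 50% below the start

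**7. Effect on the design.** None. The rule of at most 1 response in 10, then at most 5 in 29, gives an exact type I error of 0.047 at 10% response, power of 0.805 at 30%, and early termination probability of 0.736 at 10%. These agree with Section 11.4, and no restart rule enters them.

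**The case against.** The best reply is that the protocol, read as a whole, already points to Table 5. The general binimetinib rules are framed for toxicity due to that drug alone, while Section 5.3.1 is the dedicated eye section for the combination and its Table 5 interrupts both drugs. Table 6 sends RPED to Tables 3, 4 and 5 and not to Table 2. The line closing Table 2 tells investigators to prefer caution. This stands as far as it goes, and a reader who inferred that the text gives no guidance at all would be overstating the case. It is still a lean and not a rule. The allowance for toxicity-specific instructions does not settle the matter, because the Table 2 row itself names RPED.

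A second reply is that Table 4 should not count as an equal third rule. That is right. A reader might infer that two tables outvote one, but Table 4's trigger and footnote do not support that.

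Third, the gap for unimproved RPED is largely closed by the 28-day limit. This also stands, and the fix need only say so.

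Fourth, the 600 then 400 mg/day path for HCQ depends on assumptions. Two reductions is a ceiling, and Section 4.2 lets the schedule change for gastrointestinal symptoms, so a lower step such as 200 mg once daily is not strictly excluded. The path is therefore an example. The absence of any defined level does not depend on it.

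Finally, ophthalmic concerns go to the medical monitor and the drug's manufacturer (Section 10.6). That limits harm case by case but does not fix the rule.

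**Conclusion.** The point holds and should be fixed. For grade 2-3 RPED that recovers, Table 2 keeps the binimetinib dose and Table 5 lowers it by 33% or 50%, or ends it, depending on the dose at onset. Once made, a reduction is permanent. The context favours Table 5 without saying that it governs. The HCQ gap is firm: up to two reductions are allowed, no reduced level is given, and three pointers to Table 5 (one in Section 5.3, two in Section 5.3.2) are wrong.

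The conclusion rests on reading Table 5's grade 2-3 events as falling within Table 2's symptomatic row, and Table 5's grade 1 as Table 2's asymptomatic state. Table 5's own descriptions support both. How many patients would be affected cannot be estimated from the documents.

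A reader might infer that the trial's efficacy conclusion is compromised. The documents do not support that: the Simon boundaries, their error rates and the response analysis do not depend on these rules. The planned toxicity tables can also be produced as written. The cost falls on patient safety and on uniform dosing.

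**What to change.** Issue a text-only clarification amendment.

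1. **RPED and binimetinib.** State that Table 5 governs restart after grade 1-3 RPED and change the Table 2 row to match. Keep Table 4's grade 4 rule for grade 4 RPED (RVO and visual field deficit excluded, medical monitor discussion), since Table 5 has no grade 4 row. State that unresolved RPED follows the 28-day limit in Sections 5.2 and 9.4.7.
2. **RPED and HCQ.** State whether HCQ restarts or is discontinued after RPED, and bring Table 4, Table 5 and the discontinuation sentence in Section 5.3.2 into line with that decision.
3. **HCQ dose levels.** Insert a table of levels set by the sponsor, for example 600 then 400 mg/day if whole 200 mg tablets are used with at least one every 12 hours. Correct the Table 5 pointers in Sections 5.3 and 5.3.2.

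The cost is one protocol amendment, with no added patients, visits or procedures.
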